APPENDIX B. CONTRACEPTION AND PREGNANCY TESTING

Definition Related to Childbearing Potential

Women of Childbearing Potential (WOCBP) must use highly effective birth control throughout the trial including the Follow-up Period.

Women in the following categories are considered WOCBP (fertile):

1. Following menarche

- From the time of menarche until becoming postmenopausal unless permanently sterile (see below)
- A postmenopausal state is defined as no menses for 12 months without an alternative medical cause.
 - A high follicle-stimulating hormone (FSH) level in the postmenopausal range may be used to confirm a postmenopausal state in women not using hormonal contraception or hormonal replacement therapy (HRT). However, in the absence of 12 months of amenorrhea, confirmation with more than 1 FSH measurement is required.
 - Females on HRT and whose menopausal status is in doubt will be required to use one of the nonestrogen hormonal highly effective contraception methods if they wish to continue their HRT during the trial. Otherwise, they must discontinue HRT to allow confirmation of postmenopausal status before trial enrollment.
- Permanent sterilization methods (for the purpose of this trial) include:
 - Documented hysterectomy
 - Documented bilateral salpingectomy
 - Documented bilateral oophorectomy
 - For individuals with permanent infertility due to an alternate medical cause other than the above, (eg, Mullerian agenesis, androgen insensitivity, gonadal dysgenesis), Investigator discretion should be applied to determining trial entry.

NOTE: Documentation can come from the site personnel's review of the participant's medical records, medical examination, or medical history interview.

- If fertility is unclear (eg, amenorrhea in adolescents or athletes) and a menstrual cycle cannot be confirmed before first dose of IP, additional evaluation should be considered.

CONTRACEPTIVES^a ALLOWED DURING THE TRIAL INCLUDE:
Highly Effective Methods^b That Have Low User Dependency Failure rate of <1% per year when used consistently and correctly.

 • Implantable progestogen-only hormone contraception associated with inhibition of ovulation^c

 • Intrauterine device (IUD)

 • Intrauterine hormone-releasing system (IUS)^c

 • Bilateral tubal occlusion

 • Azoospermic partner (vasectomized or due to a medical cause) Azoospermia is a highly effective contraceptive method provided that the partner is the sole sexual partner of the woman of childbearing potential and the absence of sperm has been confirmed. If not, an additional highly effective method of contraception should be used. Spermatogenesis cycle is approximately 90 days.
Highly Effective Methods^b That Are User Dependent Failure rate of <1% per year when used consistently and correctly.

Combined (estrogen- and progestogen-containing) hormonal contraception associated with inhibition of ovulation^c
 
 – Oral – Intravaginal – Transdermal – Injectable

Progestogen-only hormone contraception associated with inhibition of ovulation^c
 
 – Oral – Injectable

Sexual abstinence
 
Sexual abstinence is considered a highly effective method only if defined as refraining from heterosexual intercourse during the entire period of risk associated with the IP. The reliability of sexual abstinence needs to be evaluated in relation to the duration of the trial and the preferred and usual lifestyle of the participant.)

Effective Methods^d That Are Not Considered Highly Effective Failure rate of $\geq 1\%$ per year when used consistently and correctly.

 • Progestogen-only oral hormonal contraception where inhibition of ovulation is not the primary mode of action

 • Male or female condom with or without spermicide

 • Cervical cap, diaphragm, or sponge with spermicide

 • A combination of male condom with either cervical cap, diaphragm, or sponge with spermicide (double-barrier methods)^c

^a Contraceptive use by men or women should be consistent with local regulations regarding the use of contraceptive methods for those participating in clinical studies.
 
^b Failure rate of <1% per year when used consistently and correctly. Typical use failure rates differ from those when used consistently and correctly.

^c Male condoms must be used in addition to hormonal contraception. If locally required, in accordance with Clinical Trial Facilitation Group (CTFG) guidelines, acceptable contraceptive methods are limited to those which inhibit ovulation as the primary mode of action.

^d Considered effective, but not highly effective - failure rate of $\geq 1\%$ per year.

NOTE: Periodic abstinence (calendar, symptothermal, postovulation methods), withdrawal (coitus interruptus), spermicides only, and lactational amenorrhea method (LAM) are not acceptable methods of contraception. Male condom and female condom should not be used together (due to risk of failure from friction).

APPENDIX C. CLINICAL SAFETY LABORATORY ASSESSMENTS

Laboratory Tests	Parameters	
Hematology	
 • Platelet count 	
	
 • Red blood cell (RBC) count 	
	
 • White blood cell (WBC) count with differential: neutrophils, lymphocytes, monocytes, eosinophils, basophils 	
	
 • Hemoglobin 	
	
 • Hematocrit 	
Clinical Chemistry	
 • Blood urea nitrogen (BUN) • Potassium • Creatinine • Sodium • Calcium • Glucose • Chloride • Bicarbonate • Uric acid • Albumin • C-reactive protein^a • Creatine Phosphokinase (CPK) • Triglycerides 	
 • Aspartate aminotransferase (AST) • Alanine aminotransferase (ALT) • Alkaline phosphatase (ALP) • Gamma-glutamyltransferase (GGT) • Lactate dehydrogenase (LDH) • Total and direct bilirubin • Total protein • Total cholesterol
Routine Urinalysis	
 • Specific gravity • pH, glucose, protein, blood, ketones, bilirubin, urobilinogen, nitrite, leukocyte esterase • Microscopic examination (if blood or protein is abnormal) 	
Pregnancy Testing	
 • Highly sensitive human chorionic gonadotropin pregnancy test (as needed for women of childbearing potential) (serum at screening only, urine at subsequent visits) 	

^a C-reactive protein is a pharmacodynamic marker.

APPENDIX D. INJECTION SITE REACTION ASSESSMENT TOOL

The Injection Site Assessment Tool provided in [Table 6](#) is provided as an aid in the assessment of common symptoms of injection site reaction. The Investigator may use their own judgement and description of symptoms in the assessment of injection sites following administration of IP. An Injection Site Reaction should be reported as an AE if the Investigator judges the reaction as clinically significant. A parameter grade of less than 2 is generally considered not clinically significant but the Investigator should use their judgement in the reporting of AEs. See [Section 11.2.5](#).

Table 6: Injection Site Reaction Assessment

Parameter	Grade	Description
Erythema	0	None
	1	Very slight (barely perceptible)
	2	Slight (well defined)
	3	Moderate
	4	Severe (beet redness) to slight eschar formation (injuries in depth)
Drainage	0	None
	1	Serous
	2	Serosanguinous
	3	Bloody
	4	Purulent
Edema	0	None
	1	Very slight (barely perceptible)
	2	Slight (edges well defined)
	3	Moderate (raised approximately 1 mm)
	4	Severe (raised >1 mm and beyond areas of exposure)
Induration	0	None
	1	Minimal
	2	Mild (spongy tissue)
	3	Moderate (firm, warm)
	4	Severe (hard, red, hot, crepitus)
Hematoma	0	None
	1	Minimal
	2	Mild
	3	Moderate
	4	Severe

APPENDIX E. DYSPNEA NUMERICAL RATING SCALE

On a scale from 0 to 10

Indicate how much shortness of breath you are having right now

With **0 = no shortness of breath**

And **10 = shortness of breath as bad as can be**

Circle the number:

0 1 2 3 4 5 6 7 8 9 10

Numeric rating scale assessing dyspnea

Adapted from ([Gift and Narsavage 1998](#))

6. How long did the worst attack of chest trouble last?
(Go to question 7 if you had no severe attacks)

Please tick (✓) one:

- a week or more
- 3 or more days
- 1 or 2 days
- less than a day

7. Over the past 4 weeks, in an average week, how many good days
 (with little chest trouble) have you had?

Please tick (✓) one:

- No good days
- 1 or 2 good days
- 3 or 4 good days
- nearly every day is good
- every day is good

8. If you have a wheeze, is it worse in the morning?

Please tick (✓) one:

- No
- Yes

St. George's Respiratory Questionnaire PART 2

Section 1

How would you describe your chest condition?

Please tick (✓) one:

- The most important problem I have
- Causes me quite a lot of problems
- Causes me a few problems
- Causes no problem

If you have ever had paid employment.

Please tick (✓) one:

- My chest trouble made me stop work altogether
- My chest trouble interferes with my work or made me change my work
- My chest trouble does not affect my work

Section 2

Questions about what activities usually make you feel breathless these days.

Please tick (✓) in **each box** that applies to you **these days**:

	True	False
Sitting or lying still		
Getting washed or dressed		
Walking around the home		
Walking outside on the level		
Walking up a flight of stairs		
Walking up hills		
Playing sports or games		

St. George's Respiratory Questionnaire PART 2

Section 3

Some more questions about your cough and breathlessness these days.

Please tick (✓) in **each box** that applies to you **these days**:

	True	False
My cough hurts		
My cough makes me tired		
I am breathless when I talk		
I am breathless when I bend over		
My cough or breathing disturbs my sleep		
I get exhausted easily		

Section 4

Questions about other effects that your chest trouble may have on you these days.

Please tick (✓) in **each box** that applies to you **these days**:

	True	False
My cough or breathing is embarrassing in public		
My chest trouble is a nuisance to my family, friends or neighbours		
I get afraid or panic when I cannot get my breath		
I feel that I am not in control of my chest problem		
I do not expect my chest to get any better		
I have become frail or an invalid because of my chest		
Exercise is not safe for me		
Everything seems too much of an effort		

Section 5

Questions about your medication, if you are receiving no medication go straight to section 6.

Please tick (✓) in **each box** that applies to you **these days**:

	True	False
My medication does not help me very much		
I get embarrassed using my medication in public		
I have unpleasant side effects from my medication		
My medication interferes with my life a lot		

St. George's Respiratory Questionnaire PART 2

Section 6

These are questions about how your activities might be affected by your breathing.

Please tick (✓) in **each box** that applies to you **because of your breathing**:

	True	False
I take a long time to get washed or dressed		
I cannot take a bath or shower, or I take a long time		
I walk slower than other people, or I stop for rests		
Jobs such as housework take a long time, or I have to stop for rests		
If I walk up one flight of stairs, I have to go slowly or stop		
If I hurry or walk fast, I have to stop or slow down		
My breathing makes it difficult to do things such as walk up hills, carrying things up stairs, light gardening such as weeding, dance, play bowls or play golf		
My breathing makes it difficult to do things such as carry heavy loads, dig the garden or shovel snow, jog or walk at 5 miles per hour, play tennis or swim		
My breathing makes it difficult to do things such as very heavy manual work, run, cycle, swim fast or play competitive sports		

Section 7

We would like to know how your chest usually affects your daily life.

Please tick (✓) in **each box** that applies to you **because of your chest trouble**:

	True	False
I cannot play sports or games		
I cannot go out for entertainment or recreation		
I cannot go out of the house to do the shopping		
I cannot do housework		
I cannot move far from my bed or chair		

St. George's Respiratory Questionnaire

Here is a list of other activities that your chest trouble may prevent you doing. (You do not have to tick these, they are just to remind you of ways in which your breathlessness may affect you):

- Going for walks or walking the dog
- Doing things at home or in the garden
- Sexual intercourse
- Going out to church, pub, club or place of entertainment
- Going out in bad weather or into smoky rooms
- Visiting family or friends or playing with children

Please write in any other important activities that your chest trouble may stop you doing:

.....
.....
.....
.....

Now would you tick in the box (one only) which you think best describes how your chest affects you:

- It does not stop me doing anything I would like to do
- It stops me doing one or two things I would like to do
- It stops me doing most of the things I would like to do
- It stops me doing everything I would like to do

Thank you for filling in this questionnaire. Before you finish would you please check to see that you have answered all the questions.

APPENDIX G. CAT

CAT™ Assessment
Figure 2.9

For each item below, place a mark (x) in the box that best describes you currently.
 Be sure to only select one response for each question.

EXAMPLE: I am very happy	0  1  2  3  4  5	I am very sad	Score
I never cough	0  1  2  3  4  5	I cough all the time	
I have no phlegm (mucus) in my chest at all	0  1  2  3  4  5	My chest is completely full of phlegm (mucus)	
My chest does not feel tight at all	0  1  2  3  4  5	My chest feels very tight	
When I walk up a hill or one flight of stairs I am not breathless	0  1  2  3  4  5	When I walk up a hill or one flight of stairs I am very breathless	
I am not limited doing any activities at home	0  1  2  3  4  5	I am very limited doing activities at home	
I am confident leaving my home despite my lung condition	0  1  2  3  4  5	I am not at all confident leaving my home because of my lung condition	
I sleep soundly	0  1  2  3  4  5	I don't sleep soundly because of my lung condition	
I have lots of energy	0  1  2  3  4  5	I have no energy at all	

Reference: Jones et al. ERJ 2009; 34 (3); 648-54.

TOTAL SCORE:

APPENDIX H. EXACT-PRO

The EXACT-PRO as formatted for personal digital assistant (pda)

Daily Diary

As you answer the following questions, please select the option that best describes your experience.

Exit diary **Next**

Page 1

Question 1 of 14

Did your chest feel congested today?

Not at all
 Slightly
 Moderately
 Severely
 Extremely

Back **Next**

Page 2

Info

 **Please answer this question.**

OK

Question 2 of 14

How often did you cough today?

Not at all
 Rarely
 Occasionally
 Frequently
 Almost constantly

Back **Next**

Page 3

Question 3 of 14

How much mucus (phlegm) did you bring up when coughing today?

None at all
 A little
 Some
 A great deal
 A very great deal

Back **Next**

Page 4

Question 4 of 14

How difficult was it to bring up mucus (phlegm) today?

Not at all
 Slightly
 Moderately
 Quite a bit
 Extremely

Back **Next**

Page 5

Question 5 of 14

Did you have chest discomfort today?

Not at all
 Slight
 Moderate
 Severe
 Extreme

Back **Next**

Page 6

Question 6 of 14

Did your chest feel tight today?

Not at all
 Slightly
 Moderately
 Severely
 Extremely

Back **Next**

Page 7

Question 7 of 14

Were you breathless today?

Not at all
 Slightly
 Moderately
 Severely
 Extremely

Back **Next**

Page 8

Question 8 of 14

Describe how breathless you were today:

- Unaware of breathlessness
- Breathless during strenuous activity
- Breathless during light activity
- Breathless when washing or dressing
- Present when resting

Back **Next**

Page 9

Question 9 of 14

Were you short of breath today when performing your usual personal care activities like washing or dressing?

- Not at all
- Slightly
- Moderately
- Severely
- Extremely
- Too breathless to do these

Back **Next**

Page 10

Question 10 of 14

Were you short of breath today when performing your usual indoor activities like cleaning or household work?

- Not at all
- Slightly
- Moderately
- Severely
- Extremely
- Too breathless to do these

Back **Next**

Page 11

Question 11 of 14

Were you short of breath today when performing your usual activities outside the home such as yard work or errands?

- Not at all
- Slightly
- Moderately
- Severely
- Extremely
- Too breathless to do these

Back **Next**

Page 12

Question 12 of 14

Were you tired or weak today?

- Not at all
- Slightly
- Moderately
- Severely
- Extremely

Back **Next**

Page 13

Question 13 of 14

Last night, was your sleep disturbed?

- Not at all
- Slightly
- Moderately
- Severely
- Extremely

Back **Next**

Page 14

Question 14 of 14

How scared or worried were you about your lung problems today?

- Not at all
- Slightly
- Moderately
- Severely
- Extremely

Back **Next**

Page 15

Daily Diary

You have now completed the Daily Diary. Please save your answers by selecting 'Save.'

Save

Back

Page 16

Choose

Do you really want to exit without saving?

Yes **No**

APPENDIX I. LIST OF PROHIBITED LIVE ATTENUATED VACCINES

The following list of prohibited live attenuated vaccines is indicative and is not exhaustive:

- Bacillus Calmette-Guérin antituberculosis vaccine.
- Chickenpox (Varicella).
- Intranasal influenza (FluMist-Influenza); inactive influenza vaccine delivered by injection is permitted.
- Measles (Rubeola).
- Measles-mumps-rubella combination.
- Measles-mumps-rubella-varicella combination.
- Mumps.
- Oral polio (Sabin).
- Oral typhoid.
- Rotavirus.
- Rubella.
- Smallpox (Vaccinia).
- Zostavax (for shingles; note that Shingrix is *not* live).
- Yellow fever.
- Japanese Encephalitis Vaccine (only some formulations, eg, Imojev).

APPENDIX J. ADDITIONAL SAFETY REPORTING DEFINITIONS FOR ADVERSE EVENTS OF SPECIAL INTEREST

Table 7: List of Opportunistic Infections

The following is a list of infections that are indicative of opportunistic infections, but the list is not exhaustive. Refer to Winthrop et al. 2015 for additional information (Winthrop KL et al. 2015).
	

 • Aspergillosis • Blastomycosis dermatitidis (endemic in the south-eastern and south-central states US, along Mississippi and Ohio Rivers) • Candidiasis (only systemic or extensive mucosal or cutaneous candidiasis) • Coccidioides immitis (endemic south-western US and Central and South America) • Cryptococcus • Cytomegalovirus • Herpes simplex (disseminated) 	
 • Herpes zoster (disseminated; ophthalmic; involvement of 2 or more dermatomes) • Histoplasmosis (pulmonary or disseminated; most common tropical areas Tennessee-Ohio-Mississippi river basins) • Listeriosis • Mycobacterium tuberculosis • Mycobacterium avium • Nontuberculous mycobacterium • Pneumocystis pneumonia (PCP)

Table 8: Definition of Anaphylaxis

Anaphylaxis is highly likely when any one of the following 3 criteria are fulfilled:

1. Acute onset (minutes to several hours) of certain illness with involvement of the skin or mucosal tissue, or both (eg, generalized urticaria, pruritus or flushing, swollen lips-tongue-uvula) and associated with at least one of the following:
 
 a. Respiratory compromise (eg, dyspnoea, wheeze-bronchospasm, stridor, PEF decreased, hypoxemia) b. Reduced blood pressure (BP) or associated symptoms of end-organ dysfunction (eg, hypotonia [collapse], syncope, incontinence)

2. Two or more of the following that occur after exposure to a likely allergen for that patient (minutes to several hours):
 
 a. Involvement of the skin-mucosal tissue (eg, generalized urticaria, pruritus - flushing, swollen lips-tongue-uvula) b. Respiratory compromise (eg, dyspnea, wheeze-bronchospasm, stridor, PEF decreased, hypoxemia) c. Reduced BP or associated symptoms (eg, hypotonia (collapse), syncope, incontinence) d. Persistent gastrointestinal symptoms (eg, abdominal colic, vomiting).

3. Reduced BP after exposure to known allergen for that patient (minutes to several hours); systolic blood pressure (SBP) lower than 90 mmHg or reduction from baseline greater than 30%.


Source: (Sampson et al. 2006)

APPENDIX K. DRUG-INDUCED LIVER INJURY

Drug-induced liver injury (DILI) refers to a liver injury induced by various chemical drugs, biological products, herbal medicines and their metabolites or even excipients.

1. Criteria for fulfillment of Hy's Law

Hy's Law can facilitate assessment of severe liver injury predominated by hepatocellular injury. It specifically refers to cases that meet all of the following 3 criteria:

For participants with normal liver function tests at baseline:

1. Alanine aminotransferase (ALT) or aspartate aminotransferase (AST) $\geq 3 \times$ ULN during treatment period;
2. Total bilirubin $> 2 \times$ ULN during treatment period; without cholestasis at baseline (serum alkaline phosphatase [ALP] increased);
3. No other identifiable causes explaining the simultaneous elevation of aminotransferases and total bilirubin, such as viral hepatitis A, B, C or E or other acute liver diseases, or concomitant use of other drugs that may induce liver injury.

2. Retest and confirmation

For participants with normal liver biochemistry parameters at baseline, if ALT or AST $> 3 \times$ ULN is detected, the liver-related biochemistry parameters should be retested within 48 to 72 hours whenever possible to confirm and assess the trend of changes. When ALT or AST is significantly elevated above $3 \times$ ULN (eg, ALT or AST increased to $> 5 \times$ ULN) or total bilirubin is significantly elevated above $2 \times$ ULN, immediate retest of the liver biochemistry parameters is recommended.

For participants with abnormal liver biochemistry parameters at baseline, a comprehensive evaluation should be made taking into account the above criteria, with reference to the following criteria as recommended:

1. ALT or AST $\geq 3 \times$ baseline value during treatment period;
2. An increase in total bilirubin by $1 \times$ ULN during treatment period; without cholestasis at baseline (serum ALP increased);
3. No other identifiable causes explaining the simultaneous elevation of aminotransferases and total bilirubin, such as viral hepatitis A, B, C or E or other acute liver diseases, or concomitant use of other drugs that may induce liver injury.

In addition to repeated testing of AST and ALT, liver biochemistry parameters should also include albumin, creatine kinase, total bilirubin, direct and indirect bilirubin, gamma-glutamyltransferase, prothrombin time/international normalized ratio, and alkaline phosphatase. A detailed medical history and relevant information collection are recommended, including history of alcohol use, acetaminophen, recreational drugs, various supplements, family medical history, travel history, history of contact with patients with jaundice, history of surgery, blood transfusion, liver disease or allergic diseases, history of possible occupational chemical exposure, etc. Further examinations can also include the detection of hepatitis A, B, C, D and E as well as imaging of the hepatobiliary system (such as CT, ultrasound).

All cases confirmed by repeat testing to meet the above laboratory criteria for AST/ALT and total bilirubin increased should be considered as a suspected DILI (Hy's Law) case if no other causes of liver function test abnormalities have been identified. These suspected DILI (Hy's Law) cases should be reported to the Sponsor within 24 hours.

A suspected DILI (Hy's Law) case will become a confirmed case only after all the results of the reasonable tests have been available and other etiologies have been excluded.

3. Close observation

Participants with confirmed liver injury should be closely monitored, including collecting a more detailed medical history and dynamically observing changes in the liver biochemistry parameters and coagulation function. Based on the participant's condition, liver biochemical parameters and coagulation function should be retested. Initially, liver function tests should be repeated 2 to 3 times per week. If the abnormalities stabilize or the investigational product has been discontinued and the participant is asymptomatic, the frequency of repeat testing can be reduced to once per week.

4. Follow-up

Cases with liver injury should be followed up until all abnormal parameters have recovered and stabilized at the normal or baseline level, or a relevant clinical outcome event (eg, chronic liver injury, cirrhosis, liver failure, liver transplant, death) has occurred. It should be noted that liver injury may continue evolving even after discontinuation of the related drug.

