5. OBJECTIVES AND ENDPOINTS

The primary, secondary, and exploratory objectives and endpoints are provided in [Table 2](#).

Table 2: Objectives and Endpoints

Primary Objective	Primary Endpoint

 To evaluate the efficacy of rademikibart compared to placebo as an adjunct to standard therapy on the treatment failure rate within 28 days after randomization in participants with COPD and an eosinophilic phenotype experiencing an acute COPD exacerbation. 	
 Treatment failure rate within 28 days after randomization.
Secondary Objectives	Secondary Endpoints

 To evaluate the efficacy of rademikibart compared to placebo as an adjunct to standard therapy on subsequent COPD exacerbations in participants with COPD and an eosinophilic phenotype experiencing an acute COPD exacerbation. 	
 Rate of new moderate and severe COPD exacerbations over the 28 days after randomization. Time to the first new moderate or severe COPD exacerbation in the 28 days after randomization. Mean CFB in clinical respiratory symptoms of COPD using the E-RS: COPD comprised in the EXACT-PRO through Week 1, Week 2, and Week 4. Absolute CFB in post-BD FEV₁ at Day 3, Week 1, and Week 4.

 To evaluate the safety of rademikibart compared to placebo when administered as an adjunct to standard therapy in participants with COPD and an eosinophilic phenotype experiencing an acute COPD exacerbation. 	
 Incidence of AEs, including SAEs, AESIs, and DILI reported. Incidence of UADEs. Incidence of injection site reactions. Changes in safety laboratory parameters. Changes in vital signs, physical examinations, and ECG parameters.
Exploratory Objectives	Exploratory Endpoints

 To further evaluate the efficacy of rademikibart compared to placebo as an adjunct to standard therapy on subsequent COPD exacerbations in participants with COPD and an eosinophilic phenotype 	
 Proportion of participants with at least 1 moderate or severe acute COPD exacerbation (subsequent to the index acute COPD exacerbation) through Week 4 and Week 8.

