11.3.4. Suspected Drug-induced Liver Injury

DILI refers to a liver injury induced by various chemical drugs, biological products, herbal medicines and their metabolites or even excipients. Hy's Law can facilitate assessment of severe liver injury predominated by hepatocellular injury. It specifically refers to cases that meet all of the following 3 criteria:

For participants with normal liver function tests at baseline:

1. ALT or AST $\geq 3 \times$ ULN during Treatment Assessment Period, and
2. Total bilirubin $> 2 \times$ ULN during Treatment Assessment Period; without cholestasis at baseline (serum alkaline phosphatase [ALP] increased), and
3. No other identifiable causes explaining the simultaneous elevation of aminotransferases and total bilirubin, such as viral hepatitis A, B, C or E or other acute liver diseases, or concomitant use of other drugs that may induce liver injury.

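### The Hy's Law criteria judge ALP at baseline rather than when ALT/AST and bilirubin rise, so they cannot separate hepatocellular from drug-induced cholestatic injury

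*Protocol*

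**What the plan says.** Section 11.3.4 and Appendix K, item 1, give the same three criteria and the same purpose: to help assess "severe liver injury predominated by hepatocellular injury". The criteria are introduced with "For participants with normal liver function tests at baseline" and require all of the following:

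- ALT or AST at least 3 x ULN on treatment;
- total bilirubin above 2 x ULN on treatment, "without cholestasis at baseline (serum alkaline phosphatase [ALP] increased";
- "No other identifiable causes explaining the simultaneous elevation of aminotransferases and total bilirubin".

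Section 11.3.4 repeats the ALP wording ("without cholestasis at baseline (serum alkaline phosphatase [ALP] increased), and"). Appendix K, item 2, uses it again for participants with abnormal baseline tests ("without cholestasis at baseline (serum ALP increased"), in a list offered as a recommended reference within an overall evaluation.

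At retest, Appendix K asks for a wider panel that includes "gamma-glutamyltransferase, prothrombin time/international normalized ratio, and alkaline phosphatase". A case then counts as suspected if the AST/ALT and total bilirubin criteria are confirmed and no other cause has been found. It becomes confirmed once the work-up is complete and other etiologies are ruled out. Section 11.7.3 attaches 24-hour reporting to DILI suspected of meeting Hy's Law. The related endpoint in Section 5, Table 2, is "Incidence of AEs, including SAEs, AESIs, and DILI reported".

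**The concern.** A criterion meant to pick out hepatocellular injury needs some way to recognise cholestatic injury when it happens. Here ALP is the only term that could do this, and it is assessed before any drug is given. Baseline ALP says whether cholestasis was already present. It says nothing about the pattern of an injury that develops on treatment.

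What is at stake is the meaning of a reported Hy's Law case. That label is read as a marker of severe hepatocellular injury. If it is also given to drug-induced cholestatic or mixed injury, the count no longer measures what the protocol says it measures. In a single-dose trial of about 160 participants, a hepatic summary may rest on very few cases, so how each one is labelled matters.

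**Working it through.** The protocol gives no figure to reproduce, so the check is a logical reading of the criteria.

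**Step 1: timing of each term (Section 11.3.4; Appendix K, item 1).**

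| Term | When it is judged |
|---|---|
| ALT or AST >= 3 x ULN | on treatment |
| Total bilirubin > 2 x ULN | on treatment |
| No raised ALP | baseline |
| No other cause | at the event |

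**Step 2: the ALP term in its own population.** The criteria apply to participants with normal baseline liver tests. Appendix K includes ALP in its liver biochemistry retest panel. If ALP is one of the tests that must be normal, every participant covered by the criteria has unraised baseline ALP, and the term removes none of them.

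**Step 3: two profiles differing only in ALP at the event.** The values are illustrative and are not taken from the protocol. Baseline ALP is 0.8 x ULN in both, and no other cause is found.

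| | Profile A | Profile B |
|---|---|---|
| On-treatment ALT (x ULN) | 3.2 | 3.2 |
| On-treatment bilirubin (x ULN) | 2.5 | 2.5 |
| On-treatment ALP (x ULN) | 0.8 | 4 |
| Criterion 1 (3.2 >= 3) | met | met |
| Criterion 2, bilirubin (2.5 > 2) | met | met |
| Criterion 2, baseline ALP not raised (0.8 < 1) | met | met |
| Criterion 3 | met | met |
| Label | Hy's Law | Hy's Law |

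In profile B, ALP has risen to 4 / 0.8 = 5 times its baseline and, in multiples of ULN, exceeds ALT. The label is the same as in profile A, so the classification does not depend on event-time ALP.

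**Step 4: does another provision repair this?**

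- Criterion 3 and the confirmation step remove cases with another cause. A cholestatic reaction to the study drug has no other cause, so it stays.
- ALP is remeasured at retest, but the suspected-case rule that follows names only AST/ALT and total bilirubin. The confirmation step sets no condition on ALP.

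**Step 5: the abnormal-baseline list.** The same wording has a different literal effect here. A participant whose baseline ALP is raised does not meet item 2 of that list, whatever ALT and bilirubin do later. Raised ALP alone is not named in exclusion 23 (ALT, AST and bilirubin only), although exclusion 25 allows the investigator to exclude for clinically significant chemistry findings. The list is advisory, and the suspected-case rule uses AST/ALT and bilirubin, so the case can still be captured.

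**The case against.** Four arguments can be made for leaving the text alone.

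1. *Normal liver function tests is not defined.* If the phrase covers only ALT, AST and bilirubin, as exclusion 23 might suggest, the ALP clause does some work by setting aside pre-existing cholestasis. This stands as a qualification: the claim that the clause excludes nobody depends on counting ALP. Under either reading, however, ALP at the event is not part of the rule.

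2. *Event-time ALP is available to the reviewer.* The retest panel includes it, with GGT and direct and indirect bilirubin, and hepatobiliary imaging is allowed. This is correct, so ALP may well be looked at. It remains true that no criterion says how it bears on the label.

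3. *Over-inclusion is the cautious direction for a safety trigger.* This stands for expedited reporting, and the correction should not narrow it. It does not justify giving a confirmed hepatocellular label to a cholestatic case.

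4. *The endpoint is unaffected.* A reader might infer that the Table 2 incidence is contaminated. The documents do not support that. The endpoint is reported DILI, and the protocol defines DILI broadly as drug-caused liver injury, so a drug-induced cholestatic case belongs in the count. Only its Hy's Law sub-label is in doubt.

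A reader might also infer from the abnormal-baseline list that severe hepatocellular events in people entering with raised ALP would be shut out. That too goes beyond the text. The list is advisory, the evaluation is meant to be comprehensive, and the suspected-case rule names AST/ALT and bilirubin without ALP. Section 7.5.1, item 7a, and the general AE and SAE definitions offer further routes that do not use ALP. A headcount of participants with raised baseline ALP would rest on an assumed prevalence and would count people, not misclassified cases.

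**Conclusion.** The point holds as a defect in the case definition. The criteria are stated to target mainly hepatocellular injury, but their only ALP condition is set at a time when it cannot serve that purpose. Among participants with normal baseline tests it excludes none, provided ALP is one of those tests. Whether or not ALP is included, no rule applies to ALP when ALT/AST and bilirubin rise.

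The consequence is limited to over-inclusion in the Hy's Law label: drug-induced cholestatic or mixed injury that reaches both thresholds without another cause. The number of such cases cannot be derived from the protocol. Detection in the normal-baseline group is not impaired, the DILI count is not distorted, and efficacy, type I error and power are not involved. For abnormal-baseline participants the wording needs reconciling with its purpose, but it does not by itself cause events to be missed.

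**What to change.** In Section 11.3.4 and both lists of Appendix K, replace the baseline ALP clause with a condition on ALP in the sample or samples that show the qualifying ALT/AST and bilirubin rises, and reconcile the text with the stated hepatocellular purpose. The sponsor's hepatic safety reviewer should set the limit and decide how raised baseline ALP is handled. State whether normal baseline liver tests include ALP.

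Apply the condition to the confirmed Hy's Law classification only. Leave the suspected-case trigger for 24-hour reporting on AST/ALT and total bilirubin, as Appendix K now has it.

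The cost is rewording in three places. ALP is already in the Appendix C chemistry panel and in the Appendix K retest panel, so no new sample or procedure is needed. The small downside is that mixed-pattern cases will need case-by-case review.
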